1.3 Study Objectives

The overall study objective is to assess the long-term safety and tolerability of simufilam.

This study has separate sets of objectives for the OL and RW phases. Safety and tolerability are the primary objectives of the OL phase. The primary objective of the RW phase is to assess patient response to blinded, randomized drug withdrawal.

Because drug safety in non-responders can be a critical component of a drug's risk-reward assessment, all patients who completed the 12-month OL phase were eligible to enter the RW phase, regardless of whether they previously showed an apparent response (or not) to open-label drug treatment.

Some study objectives overlap in the OL and RW phases. Hence, objectives are summarized separately below for the OL and RW phases, and for objectives spanning multiple phases. All objectives apply to mild-to-moderate Alzheimer's Disease (AD) patients, 50-85 years of age.

Objectives for the Open-label (OL) phase

- Assess the long-term safety and tolerability of OL treatment with simufilam 100 mg b.i.d. during 12-month repeat-dose oral administration.
- Assess mean changes from baseline on MMSE and compare those changes between patients with mild vs moderate AD.

Objectives for the Randomized Withdrawal (RW) phase

- Assess the safety and tolerability of treatment with simufilam 100 mg b.i.d. versus matching placebo over the 6-months study period.
- Assess patient response to blinded, randomized drug withdrawal on ADAS-Cog11.

Objectives Spanning Overall Study

Exploratory objectives tested across multiple phases are to:

- Characterize the safety and tolerability of simufilam during and up to 24 months of treatment.
- Assess mean changes from baseline on biomarkers and compare those changes between patients with mild vs moderate. For CSF biomarkers, change from baseline to M6 or M12 will be calculated. Plasma biomarkers will be analyzed for change from baseline to M6 and M12 for the OL phase and from M12 to M18 for the RW phase.

Note: All biomarker assessments in this study are exploratory endpoints that are not patient safety related, are 'Research Use Only' products, and, hence, are not intended to be compliant with FDA's Quality System Regulation (QSR) or ISO equivalent.

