Study data identified in the schedule of events are collected, and source verified, on the electronic data capture tool: Axiom Fusion eClinical Suite (Axiom, Toronto, ON, Canada).

All study data will be formulated into regulatory compliant data sets to provide transparency, traceability, and integrity of trial analysis results from the collection source. Observed study data will be mapped to the CDISC Study Data Tabulation Model (SDTM) and serve as the source data from the trial. All study analyses will be completed using analysis data sets that are derived from the SDTM and follow the CDISC Analysis Data Model (ADaM) architecture. All planned analyses will be performed using the ADaM data sets developed for this study.

The following Implementation Guides will be referenced for the configuration of SDTM and ADaM datasets:

- SDTM Model 1.7 and SDTM Implementation Guide (SDTM IG) version 3.3 will be used.
- ADaM Model 2.1 and ADaM Implementation Guide (ADaM IG) version 1.3 will be used.

Statistical Summaries

All statistical tests in all phases of the study will be two-sided and p-values of less than or equal to 0.05 will be considered statistically significant.

All p-values will be rounded and displayed in 3 decimal places. If a p-value less than 0.001 occurs, it will be shown in tables as <0.001.

Descriptive summaries of variables will be provided where appropriate. For continuous variables, the number of non-missing values (n) and the median, mean, standard deviation, minimum, and maximum will be tabulated by treatment. For categorical variables, the counts and proportions of each value will be tabulated by treatment.

Data will be presented as listings where applicable. Data not patient to analysis according to this plan will not appear in any tables or graphs but will be included in the data listings.

4 Analyses Spanning Overall Study

For the below analyses, it will be summarized by overall.

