4.7 Safety Analysis

Adverse Events

Treatment emergent AEs (TEAEs), defined as AEs that first occurred or worsened after first dose, will be summarized overall. Summary of TEAEs occuring in the Open-label phase (D1-M12 and M18-M24) will be summarized in one group . TEAEs occurring in Double-blind (RW) phase (M12-M18) will be summarized in other group. All the listings mentioned below to be provided for both the groups. The incidence of TEAEs will be reported as the number (percent) of patients with TEAEs within System Organ Class (SOC) and Preferred Term (PT). Patients will be counted only once within a SOC and PT, even if the patient experienced more than one TEAE within a specific SOC and PT. The number (percent) of patients with TEAEs will also be summarized by maximum severity and relationship. The denominators for calculating the percentages for summaries will be based on the number of patients in the analysis population enrolled to each group.

The following types of summary will be provided for Incidence of TEAEs:

- Treatment Emergent Adverse Events by System Organ Class and Preferred Term;
- Treatment Emergent Adverse Events by System Organ Class, Preferred Term and Maximum Severity;
- Treatment Emergent Adverse Events by System Organ Class, Preferred Term and Relationship to Study Drug;

The annualized incidence rate of AEs per person-years at risk, calculated as (365.25*number of AE occurrences)/(total treatment period with patients at risk of AE), will also be reported by most prevalent PT in the SOC.

The total period at risk for each patient will be defined as the period from first dose of study treatment to the date of the End of Treatment (EOT) (Month 12) or Early Termination (ET) visit for prematurely treatment discontinued patients. Annualized incidence rates will be expressed in terms of events per 100 patient years exposure.

Vital Signs

For Months 6, 12, 18, and 24, summary statistics will be provided (study population size, mean, SD, minimum, median, and maximum) for each vital sign parameter, by treatment group and overall. Summary statistics for change from baseline values will also be presented. Numbers and percentages of patients with abnormal values will be included.

ECG

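### SAP 4.7 stops a completer's time at risk at Month 12 but puts no time limit on the adverse events in the annualized rate, so events and exposure need not cover the same window

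*SAP*

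**What the plan says.** SAP section 4 is headed "Analyses Spanning Overall Study", and SAP 1.2 says version 3.0 is for the final data and the study report. Within it, SAP 4.7 defines a TEAE as an event that begins or worsens after first dose and gives no end date. It asks for an overall summary and two groups:

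- Open-label: "Summary of TEAEs occuring in the Open-label phase (D1-M12 and M18-M24) will be summarized in one group".
- RW: "TEAEs occurring in Double-blind (RW) phase (M12-M18) will be summarized in other group".

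It adds: "All the listings mentioned below to be provided for both the groups".

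An annualized rate for the most prevalent preferred terms follows, with the formula "365.25*number of AE occurrences)/(total treatment period with patients at risk of AE". The numerator carries no date limit. The next paragraph defines each patient's period at risk as "the period from first dose of study treatment to the date of the End of Treatment (EOT) (Month 12) or Early Termination (ET) visit", the second alternative being for patients who discontinue treatment prematurely.

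Two neighbouring rules do not stop at Month 12. SAP 4.6 counts days on drug from first dose to last dose, and the vital sign and laboratory summaries in SAP 4.7 run to Month 24.

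**The concern.** An incidence rate is interpretable only if its events and its person-time come from the same window. Here the events run to Month 24 and a completer's person-time stops at Month 12. SAP 1.3 makes long-term safety the overall objective and lists, among the objectives spanning the study, "Characterize the safety and tolerability of simufilam during and up to 24 months of treatment". This rate is the only AE summary in SAP 4.7 that adjusts for exposure, and SAP 1.1 allows the results to go into the study report, regulatory submissions and manuscripts. Two competent programmers could follow the same text and report materially different rates.

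**Working it through.** The plan states no AE rate or person-time, so there is no figure of its own to reproduce. The check compares person-time.

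**Per Month 24 completer, from the visit schedule alone**

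| Events counted | Months of events | Months at risk as written | Ratio |
|---|---|---|---|
| Overall (D1–M24) | 24 | 12 | 2.0 |
| Open-label (D1–M12 and M18–M24) | 12 + 6 = 18 | 12 | 1.5 |
| RW (M12–M18) | 6 | 0 of the 6 | no time at risk |

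**Study level**

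Inputs from SAP 2.5: 220 enrolled, 43 open-label dropouts, 21 who did not continue after the open-label phase. At most 220 − 43 − 21 = 156 entered RW.

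Assumptions, because the documents do not give these figures:

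- Open-label dropouts leave on average at 0.5 years (range 0.25 to 0.75).
- The 21 who did not continue each have 1.0 year.
- RW attrition is 0–30% and follow-up attrition (of those who finish RW) 0–20%. Leavers go mid-phase, at 1.25 and 1.75 years.
- The wait for RW drug supply is ignored.
- The event rate is constant. Reported rate ÷ matched rate is then person-time over which events are counted ÷ person-time defined in SAP 4.7.

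Base case (dropout at 0.5 years, no attrition after Month 12), in patient-years (PY):

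- As written: 43 × 0.5 + 21 × 1 + 156 × 1 = 198.5
- Matched, overall: 21.5 + 21 + 156 × 2 = 354.5, so 354.5 / 198.5 = 1.79
- Matched, open-label: 21.5 + 21 + 156 × 1.5 = 276.5, so 276.5 / 198.5 = 1.39

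With attrition, the result depends on whether the early-termination (ET) clause credits time beyond Month 12 (uncapped) or not (capped). At 10% in each phase, 15.6 leave in RW, 14.04 leave in follow-up and 126.36 complete:

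- Matched overall: 42.5 + 15.6 × 1.25 + 14.04 × 1.75 + 126.36 × 2 = 339.29
- Matched open-label: 42.5 + 15.6 × 1 + 14.04 × 1.25 + 126.36 × 1.5 = 265.19
- As written, uncapped: 42.5 + 15.6 × 1.25 + 14.04 × 1.75 + 126.36 × 1 = 212.93, giving 1.59 overall and 1.25 open-label
- As written, capped: 198.5, giving 1.71 and 1.34

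Over the whole grid (0.25, 0.5, 0.75 years; RW 0, 10, 20, 30%; follow-up 0, 10, 20%):

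| ET clause | Overall | Open-label |
|---|---|---|
| Uncapped | 1.37–1.83 | 1.09–1.42 |
| Capped at Month 12 | 1.55–1.83 | 1.23–1.42 |

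**If only events inside the stated period count**

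The factor is 1.0 for completers, but their time after Month 12 is lost. In the base case that is 156 / 354.5 = 44% of patient-years; over the grid it is 27–45% uncapped and 36–45% capped. Some of it is placebo time. With 1:1 randomization (SAP 2.2), 156 × 0.5 × 0.5 = 39 PY are on placebo, so the simufilam time omitted is (156 − 39) / (354.5 − 39) = 117 / 315.5 = 37%.

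**If an RW rate is produced with the single definition given**

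RW events would be divided mostly by time from D1–M12. In the base case the rate would be 78 / 156 = 0.50 of the matched rate using RW entrants' time, or 78 / 198.5 = 0.39 using all patients' time.

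**The case against.** The best defence is that events outside a defined period at risk are not events at risk. A rate limited to Day 1 to Month 12 is then internally valid, and it fits the 12-month open-label safety objective in SAP 1.3, whereas the 24-month objective is listed as exploratory. This stands as a possible reading. A reader might infer that the rates are certain to be overstated; the documents do not support that, because nothing says events after Month 12 will be counted. But nothing restricts the numerator either, and the rate sits in a section covering the whole study. The restrictive reading removes the bias for completers by discarding their exposure after Month 12.

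The ET clause can also fairly be read as applying only to patients who stop before Month 12. That removes the oddity of a late terminator having more time at risk than a completer, but it leaves the overall factor at 1.55–1.83.

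A reader might also infer that an RW rate is planned and has no valid denominator. The plan does not clearly say so: the rate is not a listing, and it is introduced apart from the three summaries itemized in SAP 4.7. The RW point is conditional.

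Nor does the Month 12 limit by itself defeat the objective "Assess the safety and tolerability of treatment with simufilam 100 mg b.i.d. versus matching placebo over the 6-months study period". The AE text in SAP 4.7 puts RW events in one group and does not split them by arm. That is a separate matter, which a corrected denominator would not change.

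**Conclusion.** The inconsistency is real, and SAP 1.2, the section 4 heading and SAP 4.6 do not repair it. What follows depends on how the text is programmed:

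- **All TEAEs counted:** the overall rate is too high whenever completers have events after Month 12. The open-label rate is too high under low to moderate later attrition. With the ET clause uncapped, leavers mid-phase and attrition split equally between RW and follow-up, the open-label direction reverses once about 58% or more of the 156 leave after Month 12. With the clause capped it does not reverse.
- **Only events in the stated period counted:** no bias for completers, but the rate says nothing about their second year.
- **RW rate, if intended:** completers contribute no time at risk within the phase.

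The per-completer ratios need only the visit schedule. The study-level factors rest on the assumed dropout timing and attrition and on a constant event rate. The patient-count TEAE tables are unaffected, and the rate is descriptive and limited to the most prevalent preferred terms. It should still be fixed, because a reported safety figure is wrong or undefined as the text stands.

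**What to change.** In SAP 4.7, delete the Month 12 qualifier and define time at risk over the same window as the events counted:

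- **Overall:** first dose to last dose or ET.
- **Open-label:** first dose to Month 12 (or Withdrawal Day 1 for those who waited for supply), plus start of Period 3 to Month 24 or ET.
- **RW, if a rate is reported:** first randomized dose to Month 18 or ET.

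Count TEAEs whose onset or worsening falls in the window; counting onset alone would drop worsening events that SAP 4.7 defines as TEAEs. State which groups get the annualized rate. State that the overall rate includes placebo time, or give simufilam-exposed time separately.

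The cost is a wording change and one derived exposure variable per window. No new data are needed: first and last dose dates are already used in SAP 4.6, and visit and ET dates are collected.

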5.3. EXCLUSION CRITERIA

Patients meeting any of the following Exclusion Criteria will be excluded from the study:

- 1. Anything that in the opinion of the Investigator would preclude participation in a 2year study.
- 2. BMI < 18.5
- 3. Positive urine drug screen.
- 4. Positive HIV, HCV or HbsAg screen.
- 5. Suicidality on C-SSRS
- 6. Exposure to an experimental drug other than simufilam, experimental biologic or experimental medical device within 3 months before screening
- 7. A medical condition that would interfere with a lumbar puncture
- 8. Residence in a skilled nursing facility and requiring 24 h care.
- 9. Clinically significant laboratory test results

- 10. Clinically significant untreated hypothyroidism (if treated, thyroid-stimulating hormone level and thyroid supplementation dose must be stable for at least 6 months before screening)
- 11. Insufficiently controlled diabetes mellitus, including requiring insulin or metformin >1000 mg/day.
- Renal insufficiency (serum creatinine > ULN and clinically significant in the opinion of PI and/or Sponsor OR eGFR <60 ml/min/m² as estimated by either the MDRD or CKD-EPI equation)
- 13. Malignant tumor within 3 years before screening (except squamous and basal cell carcinoma or cervical carcinoma in situ or localized prostate cancer or localized stage 1 bladder cancer)
- 14. History of ischemic colitis or ischemic enterocolitis
- 15. Unstable medical condition that is clinically significant in the judgment of the investigator
- 16. Alanine transaminase (ALT) or aspartate transaminase (AST) > ULN or total bilirubin > ULN and clinically significant in the opinion of PI and/or Sponsor.
- 17. History of myocardial infarction or unstable angina within 6 months before screening
- 18. History of more than 1 myocardial infarction within 5 years before screening
- 19. Clinically significant cardiac arrhythmia (including atrial fibrillation), cardiomyopathy, or cardiac conduction defect (patients with a pacemaker are acceptable)
- 20. Symptomatic hypotension, or uncontrolled hypertension
- 21. Clinically significant abnormality on screening electrocardiogram (ECG), including but not necessarily limited to a confirmed QTc (Fridericia correction method) value \geq 450 msec for males or \geq 470 msec for females.
- 22. Stroke within 18 months before screening, or history of a stroke concomitant with onset of dementia
- 23. History of brain tumor or other clinically significant space-occupying lesion on CT or MRI

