10.4. SAFETY ANALYSIS

Adverse events reported on case report forms will be mapped to preferred terms and organ systems using the MedDRA mapping system. Vital signs and clinical laboratory results will be descriptively summarized in terms of change from screening values.

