The 12-lead ECG tests will be summarized by treatment group and overall using qualitative statistics per each scheduled visit. The summary will include the number and percentage of patients with test values classified as normal, abnormal (clinically significant), abnormal (not clinically significant) and unevaluable.

Laboratory Data

For months 6. 12, 18, and 24, summary statistics will be provided (study population size, mean, SD, minimum, median, and maximum) for each laboratory test and their change from baseline by treatment group and overall, along with their change from baseline screening values will be presented overall, for each scheduled visit. Numbers and percentages of patients with abnormal values will be included.

Physical Examination

Full physical examination data will be listed overall, by enrollment group and patient only.

5 Analysis of Open-Label Phase

The following efficacy analyses will be applied to data from the OL phase (D1-M12).

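### The SAP plans only a four-category ECG table, with no QTcF values, change or outlier counts, so a small to moderate QTcF difference between the randomized arms could be missed

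*SAP*

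**What the plan says.** SAP 4.7, under ECG, reads: "The 12-lead ECG tests will be summarized by treatment group and overall using qualitative statistics per each scheduled visit". The table reports test values "classified as normal, abnormal (clinically significant), abnormal (not clinically significant) and unevaluable". No interval, change from baseline or outlier category is named there or elsewhere in the SAP.

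The neighbouring paragraphs differ. Vital signs get mean, SD, median, minimum and maximum at Months 6, 12, 18 and 24, and "Summary statistics for change from baseline values will also be presented". Laboratory tests are handled likewise, and both also get counts of abnormal values.

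SAP 1.3 lists as an RW-phase objective: "Assess the safety and tolerability of treatment with simufilam 100 mg b.i.d. versus matching placebo over the 6-months study period".

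The protocol mentions QTc once, in exclusion criterion 21 of section 5.3: "Clinically significant abnormality on screening electrocardiogram (ECG), including but not necessarily limited to a confirmed QTc (Fridericia correction method) value", with limits of 450 ms or more for males and, for females, at or above "470 msec for females". Protocol 10.4 plans no ECG analysis. It says only: "Vital signs and clinical laboratory results will be descriptively summarized in terms of change from screening values".

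**The concern.** Months 12 to 18 are the study's only placebo-controlled period. Every version of the schedule places an ECG at each end of it. This is the one place where the trial can separate a drug effect on the ECG from ageing, disease and concomitant medication.

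A reader category is a blunt tool for that. It pools rhythm, conduction, repolarisation and other findings into one judgement, and it moves only when an individual crosses a reader's line. Patients with long QTcF were excluded at entry, so a modest average prolongation would leave most patients in the category they were already in. The arms could show similar counts while their mean QTcF differed by several milliseconds. The report would then offer little on QTc for a drug whose long-term safety is the study's overall objective.

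**Working it through.** **No figure to reproduce.** Neither document gives a power, precision or detectable difference for ECG, and Protocol 10.5 contains no sample-size calculation.

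**Inputs from the documents**
- SAP 2.5: 220 enrolled, 43 dropped out in the open-label phase, 21 did not reconsent. At most 220 − 43 − 21 = 156 could enter RW.
- SAP 2.2: 1:1 randomization, so at most about 156 / 2 = 78 per arm.
- Protocol 5.3: 450 ms (male) and 470 ms (female).
- Protocol 7.2.7 and 7.2.8: the Month 12 and Month 18 ECGs are both listed after the dose. Both arms are on simufilam at Month 12, so a drug effect would appear as a difference between arms in the Month 12 to 18 change.

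**Assumed, not in the documents:** SD of QTcF change 12 to 25 ms; male mean 410 to 430 ms, female mean 10 ms higher; cross-sectional SD 15 to 25 ms; equal sexes; a QTcF at or above the limit is read as abnormal. Two-sided 5% is used for illustration only, since no ECG test is planned.

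**Precision of a numeric summary.** Half-width = 1.96 × SD × √(2/n), with √(2/78) = 0.1601.
- SD 12: 1.96 × 12 × 0.1601 = 3.8 ms
- SD 25: 1.96 × 25 × 0.1601 = 7.8 ms
- With 15% missing (an assumption; 66 per arm): 4.1 to 8.5 ms

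**Sensitivity, numeric scale.** Power = Φ(δ / (SD × √(2/n)) − 1.96). For δ = 10 and SD = 25: 10 / 4.00 − 1.96 = 0.54, giving 70%. For δ = 5 and SD = 12: 5 / 1.92 − 1.96 = 0.64, giving 74%.

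**Sensitivity, share at or above the limits.** Take male mean 420, female 430, SD 20. Without a shift the share is ½[1 − Φ(1.5)] + ½[1 − Φ(2)] = 4.5%. With a 10 ms shift it is ½[1 − Φ(1)] + ½[1 − Φ(1.5)] = 11.3%. That is 78 × 0.068 = 5.3 extra patients in an arm. Power = Φ{(|p₁ − p₀| − 1.96√[2p̄(1 − p̄)/n]) / √[(p₀(1 − p₀) + p₁(1 − p₁))/n]} = 35%.

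Over the assumed ranges, at 78 per arm:

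| True mean difference | Mean QTcF change | Share at or above 450/470 ms |
|---|---|---|
| 5 ms | 24% to 74% | 5% to 18% |
| 10 ms | 70% to 99.9% | 12% to 62% |
| 20 ms | 99.9% or more | 53% to 99.9% |

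The two columns rest on different assumptions (SD of change; level and spread), so their ends should not be paired. The last column ignores the entry exclusion, which probably flatters it. It also treats the category as a pure QTcF cut. If the category instead pools all findings, with an assumed 30% background abnormal rate, a 5-point rise has about 10% power.

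**The case against.** A reader might infer that the SAP contradicts the protocol by discarding a numeric QTcF criterion. The documents do not support that. "a confirmed QTc (Fridericia correction method) value" appears only as one example of a clinically significant screening abnormality. Protocol 7.1 has no QTc stopping rule and Protocol 10.4 promises no ECG analysis, so the SAP drops nothing that was planned.

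A reader might also infer that any QTc shift would go undetected. That is too strong. There are four categories, clinically significant findings are separated from the rest, and the table is by treatment group. A 20 ms shift could well show.

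Other points also have weight. The ECG summary is descriptive, so power is only a yardstick. All QTcF inputs above are assumed. No passage says that intervals were recorded after screening, and the visit lists mention neither replicate nor central reading. Protocol 2.2 reports a negative hERG test and no adverse ECG effect in dogs, and a DSMB reviews safety.

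These points limit the size of the concern but do not remove it. The backstops do not supply a comparison between arms. Listings of eCRF data (SAP 3.2) compare nothing. The general rule for continuous variables (SAP 3.2) is not tied to QTc. Post-hoc analyses (SAP 1.1) are optional. SAP 4.7 describes RW-phase adverse events as one group and states no split by arm.

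**Conclusion.** The point holds as a low-cost improvement. The planned ECG output is categorical only, and a small to moderate QTcF difference between the randomized arms (around 5 to 10 ms in the illustration) could be missed. A large one might still be visible.

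The direction is firm: at 5 and 10 ms the numeric scale is the more sensitive throughout the assumed ranges. The exact percentages are not firm, because they depend on QTcF means and SDs that the documents do not give. The most useful figure is the CI half-width of about 4 to 8 ms at 78 per arm. With that precision even a null result would be informative, which four counts are not. It rests on the assumed SD of change, on the maximum RW size of 156, and on intervals being available.

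**What to change.** In SAP 4.7, keep the categorical table. Where ECG intervals were captured, or can be transcribed from the ECG reports, add:
- QTcF and heart rate by randomized arm: n, mean, SD, median, minimum, maximum.
- Change from the last ECG at or before RW start to Month 18, with a 95% CI for the arm difference. That starting ECG is Month 12 for everyone, because the Withdrawal Day 1 visit has no ECG (Protocol 7.2.9 and Appendix A). State how long before RW start it was taken in patients who waited for drug supply.
- Counts at or above 450 ms (male) and 470 ms (female) by arm.

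Label any change from Day 1 as descriptive: the Day 1 ECG is pre-dose and later ECGs are listed after dosing, so that change mixes a dosing effect with time.

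If intervals were not captured and cannot be retrieved, state in the report that the study cannot assess QTc.

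Reconcile the ECG schedule as well. Protocol section 4 includes Months 3 and 9. Protocol 7.2.4, Appendix A and SAP 2.2 do not. SAP Table 1 marks Months 3, 9, 15 and 21. This decides whether the RW phase has a Month 15 ECG.

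Cost: one extra descriptive table and possibly some transcription. No new visit or hypothesis is needed.
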